6.1.1 Source Documents

The PI will permit trial-related monitoring, audits, IRB review, and regulatory inspection(s), providing direct access to source documents.

6.1.2 Case Report Forms

Data may be entered from the source documents directly into eCRFs in C3D for each patient enrolled in this study. The principal investigator or research nurse will review the eCRFs for completeness and accuracy. Site personnel may also conduct independent audits to ensure completeness and accuracy of data in C3D.

Only the following adverse events will be recorded on the Case Report Form:

- Grade 2 unexpected events that are possibly, probably or definitely related to the study drugs;
- Grade 3 and 4 events that are possibly, probably or definitely related to the study drugs;
- Grade 5 events regardless of attribution;
- Serious Events regardless of attribution.

Patients who meet the standard of care criteria for resection of their disease will undergo a major operative procedure and may receive extensive care in the ICU. The principal investigator or designee will closely monitor and document the clinical care and treatment of each patient as per standard of care at the NIH Clinical Center. As per NIH Clinical Center standards of practice, the Occurrence Reporting System will be used to report any clinical events meeting these reporting criteria.

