1 INTRODUCTION

1.1 STUDY OBJECTIVES

1.1.1 Primary Objective:

- To determine the progression-free survival (PFS) on first-line therapy in patients with NETs of the gastrointestinal tract and pancreas treated with sunitinib or everolimus based on tumor genotyping.

1.1.2 Secondary Objectives:

- To determine overall response rate (ORR; i.e., sum of complete response [CR], partial response [PR], and stable disease [SD]) and duration of response
- To determine overall survival and median survival time (MST)
- To evaluate any relationship between tumor genotype, treatment and PFS
- Safety endpoints (i.e. AEs, clinical laboratory evaluations, ECGs, physical examination findings, and vital sign measurements).

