6 DATA COLLECTION AND EVALUATION

6.1 DATA COLLECTION

The PI will be responsible for overseeing entry of data into a password protected electronic system (NCI C3D) and ensuring data accuracy, consistency and timeliness. Clinical data will be entered into the NCI C3D electronic database at least once every two weeks when patients are enrolled on the trial. Protocol-specific eCRFs will be developed for this trial in C3D. The principal investigator, associate investigators/research nurses and/or a contracted data manager will assist with the data management efforts.

All data obtained during the conduct of the protocol will be kept in secure network drives or in approved alternative sites that comply with NIH security standards. Primary and final analyzed data will have identifiers so that research data can be attributed to an individual human subject participant.

The NCI investigators will be responsible for the collection, maintenance, and quality control of the study data.

Labmatrix will be used for sample data collection. Data in this system will be entered by the NCI staff.

All adverse events, including clinically significant abnormal findings on laboratory evaluations, regardless of severity, will be followed until return to baseline or stabilization of event. Patients will be followed for adverse events for at least 30 days after removal from study treatment or until off-study, whichever comes first.

An abnormal laboratory value will be recorded in the database as an AE **only** if the laboratory abnormality is characterized by any of the following:

- Results in discontinuation from the study
- Is associated with clinical signs or symptoms
- Requires treatment or any other therapeutic intervention
- Is associated with death or another serious adverse event, including hospitalization.
- Is judged by the Investigator to be of significant clinical impact
- If any abnormal laboratory result is considered clinically significant, the investigator will provide details about the action taken with respect to the test drug and about the patient's outcome.

End of study procedures: Data will be stored according to HHS, FDA regulations and NIH Intramural Records Retention Schedule as applicable.

Loss or destruction of data: Should we become aware that a major breach in our plan to protect subject confidentiality and trial data has occurred, the IRB will be notified.

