7.2.2 NIH Intramural IRB Requirements for PI Reporting at Continuing Review

The protocol PI will report to the NIH Intramural IRB:

1. A summary of all protocol deviations in a tabular format to include the date the deviation occurred, a brief description of the deviation and any corrective action.
2. A summary of any instances of non-compliance
3. A tabular summary of the following adverse events:
 - All Grade 2 **unexpected** events that are possibly, probably or definitely related to the research;
 - All Grade 3 and 4 events that are possibly, probably or definitely related to the research;
 - All Grade 5 events regardless of attribution;
 - All Serious Events regardless of attribution.

NOTE: Grade 1 events are not required to be reported.

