80% and 95% confidence intervals to explore whether the present results exceed those from prior studies. In addition, the Kaplan-Meier curves for all patients who received either sunitinib and everolimus as their treatments may be combined into one pooled Kaplan-Meier curve if the two curves for these treatments are sufficiently similar to one another ($p > 0.30$ by a two-tailed log-rank test). This combined curve will then be evaluated relative to the published median of 11 months PFS for each arm to provide a more powerful comparison relative to the historically expected results. In addition, Kaplan-Meier curves limited to the patients who received targeted therapy based solely on mutation status may be constructed for exploratory and descriptive purposes.

Response and overall survival will also be evaluated as secondary endpoints, based on the patients treated with sunitinib or everolimus, using all patients receiving treatment. These results will be descriptive and may consist of fractions of responses as well as Kaplan-Meier curves for survival. The association between genotype and PFS will be explored by evaluating the results within a treatment based on the major genotype categories identified. Safety will be evaluated by tabulating and reporting the distribution of the worst grade of each type of toxicity found, per patient, separately by arm. Should any particular type of toxicity result in 5 or more patients with grade 3-4 toxicity, a comparison of the distributions of toxicity between the two arms may be performed using a Cochran-Armitage test for trend.

Because the patients may not end up being assigned in equal proportions to the two arms, and because the goal is to have 44 evaluable patients who have received each treatment, additional patients beyond the 44 described above may be enrolled on the arm with faster accrual. As such, the study will have an accrual ceiling of 120 patients, with accrual ending when there are 44 evaluable patients on the arm with fewer patients. An amendment may also be needed if a lower proportion of patients than expected receive study drug therapy or if a high portion of treated patients are not evaluable for response. It is anticipated that 20-30 patients per year may enroll onto this trial; thus, accrual may be completed in 4-5 years.

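### The adverse-event list in 6.1.2 would not supply all the grades that the Section 8 worst-grade toxicity table calls for

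*Combined protocol and SAP*

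**What the plan says.** Safety is a secondary objective, stated in 1.1.2 without a grade limit: "Safety endpoints (i.e. AEs, clinical laboratory evaluations, ECGs" and further items. Section 8 says it will be evaluated by "tabulating and reporting the distribution of the worst grade of each type of toxicity found, per patient, separately by arm". Once a type of toxicity has reached grade 3-4 in 5 or more patients, "a comparison of the distributions of toxicity between the two arms may be performed using a Cochran-Armitage test for trend". Section 8 does not say which records feed the table, and it sets no lower grade and no attribution requirement.

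Section 6.1.2 governs recording: "Only the following adverse events will be recorded on the Case Report Form". The list has four entries. The grade 2 entry reads "Grade 2 unexpected events that are possibly, probably or definitely related to the study drugs". The others are grade 3-4 events at least possibly related to study drug, all grade 5 events, and all serious events.

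Nearly the same list appears in 7.2.2 for continuing review by the IRB, with "NOTE: Grade 1 events are not required to be reported". Section 6.1 says that all adverse events "regardless of severity, will be followed until return to baseline or stabilization of event". That sentence concerns follow-up, not entry. Under 6.3.1, every patient is evaluable for toxicity from first treatment.

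**The concern.** A list suited to IRB summaries has been made the general recording rule, while the analysis section asks for a full grade distribution. A table built from those records would show too few patients at grades 1-2 and too many with no event of that type. A trend test across all grades would score those patients as unaffected.

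A reader of the results could not tell a toxicity that was absent from one that was not collected. For two drugs given daily until progression, low-grade toxicity is a real part of the safety picture.

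**Working it through.** The plan states no figure for this point, so there is none to reproduce. The check sets the recording rule against the table and then sizes the gap.

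**1. What the table needs and what the list supplies**

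| Event class | In scope of the Section 8 table | On the 6.1.2 list |
|---|---|---|
| Grade 1, non-serious | yes | no |
| Grade 2, non-serious, expected or unrelated | yes | no |
| Grade 2, related and unexpected | yes | yes |
| Grade 3-4, non-serious, unrelated | yes | no |
| Grade 3-4, related | yes | yes (laboratory events: see step 5) |
| Grade 5, or serious at any grade | yes | yes |

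**2. Where the missing patients would go.** All treated patients are in the denominator (6.3.1), and no category for events not collected is defined. In a CRF-based table, a patient whose worst event of one type is unrecorded therefore falls among those without that type. This holds type by type: unrecorded grade 1 diarrhea does not hide recorded grade 3 fatigue in the same patient.

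**3. Size.** Section 1.2.3.3 gives all-grade and grade 3-4 rates for sunitinib from one analysis, so the two can be subtracted. Patients with grade 1-2 only = (all-grade rate - grade 3-4 rate) x 44, where 44 is the target per arm.

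| Toxicity | All grades | Grade 3-4 | Share at grade 1-2 only | Of 44 patients |
|---|---|---|---|---|
| Hand-foot skin reaction | 19% | 5% | 14/19 = 74% | 0.14 x 44 = 6.2 |
| Dry skin | 16% | 1% | 15/16 = 94% | 0.15 x 44 = 6.6 |
| Skin discoloration | 28% | none | 100% | 0.28 x 44 = 12.3 |

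These are upper figures, because serious events and unexpected related grade 2 events are recorded. Section 8 has an "accrual ceiling of 120 patients, with accrual ending when there are 44 evaluable patients on the arm with fewer patients", so a faster-accruing sunitinib arm could reach 120 - 44 = 76. The counts would then be 0.14 x 76 = 10.6, 0.15 x 76 = 11.4 and 0.28 x 76 = 21.3. For everolimus, 4.1.2 says that most events were grade 1-2, so the direction is the same. The documents give no matched all-grade and grade 3-4 rates for it, so no count is given.

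**4. Effect on a trend test.** Section 8 gives no scores. Assume 0 for none and the grade number otherwise; the test then compares mean scores between arms. For hand-foot reaction, grade 1-2 events add between 0.14 x 1 = 0.14 and 0.14 x 2 = 0.28 to the sunitinib mean, and grade 3-4 events add between 0.05 x 3 = 0.15 and 0.05 x 4 = 0.20. Dropping all grade 1-2 events removes between 0.14/(0.14 + 0.20) = 41% and 0.28/(0.28 + 0.15) = 65% of the score. For dry skin the range is 0.15/(0.15 + 0.04) = 79% to 0.30/(0.30 + 0.03) = 91%.

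The trigger must be met first. The expected number of sunitinib patients with grade 3-4 is 0.05 x 44 = 2.2 for hand-foot reaction and 0.01 x 44 = 0.4 for dry skin, so these toxicities may never be tested. For them the main damage is to the table.

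**5. Other recording rules**

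- Rash must be reported as an AE (4.1.2.2, directly after the grade 1 sentence, among the everolimus toxicities).
- Laboratory abnormalities enter the database on criteria that do not depend on grade, such as needing treatment (6.1). Section 4.1.2.8 directs medical therapy for grade 1 and 2 metabolic events, so some low-grade events would be entered.
- The same laboratory rule can leave out untreated, asymptomatic grade 3-4 abnormalities. The footnote to Table 5 lets patients with grade 3 or 4 lymphopenia continue without interruption.
- Appendix E sends blood pressure data and CTCAE grade changes to the CRF or the blood pressure diary.

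None of these rules is mentioned in 6.1.2, which says that only its own list is recorded.

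**The case against.** The strongest reply is that the misclassification is inferred. Section 8 does not say that the table comes from the CRF, and it defines no category for patients without an event. A table of recorded events, footnoted as such, would satisfy both sections. The visit schedule (3.4) lists adverse events and the patient diaries (Appendix F) have a side-effects column, so source data exist. Both drugs are commercial, and a short list may be a deliberate saving of effort. The trend test is optional, and the arms are set by genotype, so any comparison between them is already non-randomised.

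Much of this stands. The consequence has to be stated conditionally, and its importance is limited. But the plan neither specifies the footnoted table nor directs that source or diary entries be used. The word toxicity might be read as related events only. The unrelated grade 3-4 events would then be no loss, but the low-grade gap would remain.

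Three stronger readings are tempting, and the documents do not support them.

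- A reader might infer that most low-grade events of every kind are lost. The rash, laboratory and blood pressure rules may supply some of them. The gap is clearest for clinical toxicities with no rule of their own, such as diarrhea, fatigue, stomatitis and hand-foot reaction.
- A reader might infer much larger losses from 11.1.2, for example (52.4% - 6.3%) x 44 = 20 patients for diarrhea. That subtracts a treatment-related rate from a treatment-emergent one. The neutropenia figures there also conflict: 0.3% at grade 3 and 3.2% at grade 4 against 13.5% at grades 3 to 5, which would leave 10.0% at grade 5 when all grade 5 events total 1.6%.
- A reader might infer that related grade 3 and higher events are complete. The laboratory rule in 6.1 means that they may not be.

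**Conclusion.** The mismatch is in the text: the only general adverse-event recording rule does not supply what the Section 8 table asks for. If that table is built from the CRF, it understates grade 1-2 clinical toxicity by type, by up to about 6, 7 and 12 of 44 sunitinib patients for hand-foot reaction, dry skin and skin discoloration. Any all-grade trend test that is run would use truncated data.

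The counts assume that the published rates carry over to this trial, that the events are non-serious, and that any at grade 2 count as expected. Expectedness depends on investigator brochures that are not in the documents. The 5-patient trigger is affected only through non-serious unrelated grade 3-4 events and laboratory events that fail the 6.1 criteria. The primary PFS analysis is unaffected. The plan should be changed on this point, but the trial's main conclusion does not depend on it.

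**What to change.** Name the data source of the safety table in Section 8, and adopt one of two options.

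(a) Limit the table and any between-arm test to recorded treatment-related events of grade 3 and higher, and label them so. State that laboratory events are included only if they meet the 6.1 criteria, or derive laboratory grades from the collected values. List unrelated grade 5, other serious and unexpected grade 2 events separately. The cost is wording in Section 8 and 6.1.2, plus programming if laboratory grades are derived. The downside is that low-grade toxicity is not summarised.

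(b) Amend 6.1.2 to record all grades of events at least possibly related to study drug, keeping all grade 5 and all serious events. The worst-grade table, labelled as related events, and the trend test can then stand. The cost is a protocol and CRF amendment, more data entry, and recovery of earlier low-grade events from source.

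Under either option, state in 6.1.2 how the rash rule (4.1.2.2), the laboratory rule (6.1) and the blood pressure rules (Appendix E) relate to its list.

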5 BIOSPECIMEN COLLECTION

5.1 SAMPLE COLLECTION FOR GENOTYPING AND RESEARCH STUDIES

5.1.1 Tumor Sample

Within 4 weeks prior to initiation of treatment with the respective study agent (everolimus or sunitinib), patients who meet eligibility criteria, will undergo biopsy of the primary tumor or any metastatic site for molecular analyses. Patients will undergo a percutaneous core needle (16 or 18 gauge) biopsy of the tumor under local anesthesia if there are no paraffin blocks available of tumor sample previously removed or biopsied. These percutaneous biopsies will be performed by interventional radiology (CT scan or ultrasound guidance). If needed, patients will be offered conscious sedation for the biopsy procedure. Sample collection will be performed according to standard operating procedures. Four core needle biopsies will be obtained, three samples will be formalin fixed and sent to the Laboratory of Pathology in the NCI for histological study. The official pathology report and samples will then be taken to [name] laboratory:

[name], Email: [contact]

CANCER GENETICS BRANCH

[name],

[name],

[contact]

The remaining sample will be immediately placed in cryovials, snap frozen on liquid nitrogen or dry ice and transported to [name] laboratory.

Fresh tissue samples should be collected into empty, unused cryovials (Nunc catalog #5001-0012, 5001-1020 or equivalent) on dry ice or liquid nitrogen. Samples may be obtained by FNA or core biopsy.

The interval between sample acquisition and freezing on dry ice must not exceed 30 minutes. Frozen, vialled samples should be transferred from dry ice to -80°C (minimum) or liquid nitrogen frozen storage within 2 hours.

Samples will be recorded in LabMatrix and reviewed by the Laboratory of Pathology to confirm the diagnosis. The remaining sample will be transported to [name] laboratory [[name]., [name], [name], [contact], Email: [contact]] for tumor genotyping along the saliva DNA.

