6.3.1 Definitions

Evaluable for toxicity: All patients will be evaluable for toxicity from the time of their first treatment with sunitinib or everolimus.

Evaluable for objective response: Only those patients who according to RECIST guideline (version 1.1) have measurable disease present at baseline, have been started on therapy with everolimus or sunitinib, and have had their disease re-evaluated will be considered evaluable for response. These patients will have their response classified according to the definitions stated below. (Note: Patients who exhibit objective disease progression prior to the end of cycle 1 will also be considered evaluable.)

Evaluable Non-Target Disease Response: Patients who have lesions present at baseline that are evaluable but do not meet the definitions of measurable disease, have been started on therapy with everolimus or sunitinib, and have had their disease re-evaluated will be considered evaluable for non-target disease. The response assessment is based on the presence, absence, or unequivocal progression of the lesions.

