7 SAFETY REPORTING REQUIREMENTS/DATA AND SAFETY MONITORING PLAN

7.1 DEFINITIONS

7.1.1 Adverse Event

Any untoward medical occurrence in a human subject, including any abnormal sign (for example, abnormal physical exam or laboratory finding), symptom, or disease, temporally associated with the subject's participation in research, whether or not considered related to the subject's participation in the research.

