10.4.1.1.3 Risk of Radiation

This research study involves exposure to radiation from one CT guided biopsy. This radiation exposure is not required for medical care and is for research purposes only. The amount of radiation received in this study is 0.80 rem which is below the guideline of 5 rem per year allowed for research subjects by the NIH Radiation Safety Committee. The average person in the

United States receives a radiation exposure of 0.3 rem per year from natural sources, such as the sun, outer space, and the earth's air and soil. More information about radiation is available in the pamphlet, An Introduction to Radiation for NIH Research Subjects.

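### The case report form ties unexpected grade 2 and grade 3-4 events to the study drugs, while the IRB table needs the same grades tied to the research, so some non-serious biopsy harm stays out of the trial database

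*Combined protocol and SAP*

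**What the plan says.** Section 6.1.2 opens its list with "Only the following adverse events will be recorded on the Case Report Form". Four categories follow. The first two carry a drug-attribution condition: "Grade 2 unexpected events that are possibly, probably or definitely related to the study drugs" and "Grade 3 and 4 events that are possibly, probably or definitely related to the study drugs". The other two, grade 5 events and serious events, carry none.

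Section 7.2.2 sets out the table that the investigator gives the IRB at continuing review. It has the same four categories, but grades 2 to 4 are attributed differently: "All Grade 3 and 4 events that are possibly, probably or definitely related to the research", with unexpected grade 2 events worded to match. Section 7.1.1 is also broad, defining an adverse event as one "temporally associated with the subject's participation in research".

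The biopsy is described in 5.1.1. Patients with no stored tumor block have a percutaneous core biopsy in the 4 weeks before treatment, and "Four core needle biopsies will be obtained". Patients with a known familial syndrome are exempt (2.1.1.4, 2.4). Section 10.4.1.1.2 lists bleeding, infection and injury to viscera as risks. Of the radiation from the CT-guided procedure, 10.4.1.1.3 says: "This radiation exposure is not required for medical care and is for research purposes only".

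**The concern.** A complication that appears after the biopsy and before the first dose cannot be attributed to a drug not yet given. The drug condition in 6.1.2 therefore excludes it from the CRF unless it is serious or fatal, while 7.2.2 still expects some of these events to be reported.

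Two things are at stake. The first is the protocol's own reporting duty, because the database would not contain everything that the IRB table calls for. The second is the safety picture of the genotype-guided strategy. For patients without archival tissue the biopsy is part of that strategy, and section 8 foresees a larger randomized trial if progression-free survival looks improved. A safety summary built from the CRF would contain no non-serious biopsy complication of these kinds, and a reader could not tell whether none occurred or the rule left them out.

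**Working it through.** The plan gives no figure to reproduce and no arithmetic applies. The check has two parts.

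**1. The two lists side by side, for an event caused by the biopsy and not by a drug.**

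| Biopsy-related event | On the CRF (6.1.2)? | In the IRB table (7.2.2)? |
|---|---|---|
| Grade 1, non-serious | No | No |
| Grade 2, expected, non-serious | No | No |
| Grade 2, unexpected, non-serious | No | Yes |
| Grade 3-4, non-serious | No | Yes |
| Serious, any grade | Yes | Yes |
| Grade 5 | Yes | Yes |

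The lists disagree in exactly two rows: unexpected grade 2, and non-serious grade 3-4.

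**2. Whether any other text puts those two kinds of event on the CRF.**

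- Section 6.1 has all adverse events followed to resolution or stabilization. Following an event is not the same as entering it on the CRF, and this does not override the closed list.
- Section 6.1 also sends certain laboratory abnormalities to the database without a drug condition, for example those needing treatment. That covers a laboratory finding after a biopsy but not a clinical complication. It also sits awkwardly with the closed list in 6.1.2.
- The study calendar (3.4) lists adverse events at Cycle 1 Day 1, within 2 weeks before treatment. It schedules the inquiry and leaves the CRF rule unchanged.
- Section 6.1.3 checks source documents against the electronic CRF. Leaving out a non-serious biopsy event complies with 6.1.2, so this check need not flag it.
- Sections 7.1.10 and 7.2.1 send unanticipated problems to the IRB. That route also requires a greater risk than was previously known, and it is not a CRF entry.
- Section 8 tabulates worst toxicity per patient by arm and has no line for procedural harm.

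None of these closes the gap for non-serious clinical complications of the biopsy.

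**The case against.** The strongest reply is that the restriction binds the CRF and nothing else. Section 7.2.2 is a separate duty on the investigator and does not say that its table is drawn from the CRF. An investigator who follows it as written must report a non-serious grade 3 biopsy event, taking it from source notes if need be. The team meets weekly and the principal investigator reviews adverse events for each patient (7.4.1). This stands. A reader might infer that such harm goes unrecorded everywhere, or that the IRB table must come out empty. The documents do not support either inference.

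The affected set is also small. The protocol's own toxicity tables describe grade 4 as life-threatening, which would generally be serious under 7.1.5 and so recorded. That section also allows important medical events that may need intervention to count as serious, which could take in many grade 3 bleeds or organ injuries. Few grade 2 events are likely to be unexpected, since the main biopsy risks are already described. What remains is mainly non-serious grade 3 events and the occasional unexpected grade 2 event. This stands too.

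A reader might take section 6.3.1, "All patients will be evaluable for toxicity from the time of their first treatment with sunitinib or everolimus", as barring the recording of anything before the first dose. It does not. It sits under the response criteria and defines who is evaluable for toxicity. It sets no recording window, and 6.1.2 gives no start date. The exclusion comes from the attribution wording alone.

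None of this reconciles the two lists. It limits the consequence but leaves the CRF rule narrower than the duty it should serve.

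**Conclusion.** The mismatch is real and follows from the wording without any assumption. Two categories that 7.2.2 requires are barred from the CRF by 6.1.2 when the cause is the research biopsy: unexpected grade 2 events and non-serious grade 3-4 events. The database therefore cannot by itself supply the IRB table, and safety summaries drawn from it would omit these events. That last step assumes the summaries are built from the CRF, which is the ordinary course but is not stated.

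The consequence is modest. Serious and fatal events are recorded whatever their cause, source records may hold the rest, and neither progression-free survival nor power is touched. A reader might want a count of missed events or a bound on the complication rate. The documents support neither: they give no number of patients needing a new biopsy and no expected complication rate, and the plan makes no inference about one. This is a wording conflict worth correcting because it is cheap to correct and makes the safety data more complete.

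**What to change.** In the first two bullets of 6.1.2, replace the attribution to the study drugs with: *related to the research (study drugs or research procedures, including the tumor biopsy)*. Add a sentence saying that recording starts at the first research procedure. This brings the CRF into line with 7.2.2.

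The cost is a few more CRF entries, with no added visits or procedures. Events attributed only to the biopsy should be identifiable as such, so that they are not read as drug toxicity in the by-arm table of section 8. A separate line for biopsy complications, with biopsied patients as the denominator, would be useful but is optional, since no stated objective requires it.
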